### 20.4. Causality

The investigator must assign causality to each adverse event in relation to the IMP based on the following definitions:

---

**Not related:** AE with an incompatible time relationship to IMP administration, and that could be explained by underlying disease or other drugs or is incontrovertibly not related to the Investigational Product

**Possibly related:** AE with a reasonable time relationship to IMP administration, but which also could be explained by concurrent disease or other medications.

**Probably related:** AE with a reasonable time relationship to IMP administration that is unlikely to be attributed to concurrent disease or other medications.

**Definitely related:** AE with plausible time relationship to IMP administration and which cannot be explained by concurrent disease or concomitant medications.

## 20.5. Severity (Intensity) of adverse event

Grade refers to the intensity of an AE and should not be confused with seriousness

**Grade 1** Mild; asymptomatic or mild symptoms; clinical or diagnostic observations only; intervention not indicated.

**Grade 2** Moderate; minimal, local or noninvasive intervention indicated; limiting age appropriate instrumental Activities of Daily Living (ADL\*).

**Grade 3** Severe or medically significant but not immediately life-threatening; hospitalisation or prolongation of hospitalisation indicated; disabling; limiting self-care ADLs.

**Grade 4** Life-threatening consequences; urgent intervention indicated.

**Grade 5** Death related to AE.

## 20.6. Serious adverse event

A serious adverse event (SAE) is any untoward medical occurrence or effect that, at any dose:

- Results in death,
- Is life-threatening.

Life-threatening in the definition of serious refers to an event in which the participant was at risk of death at the time of the event, it does not refer to an event which hypothetically might have caused death if it were more severe.

- Requires inpatient hospitalisation or prolongation of existing hospitalisation.

Hospitalisation is defined as inpatient admission or care regardless of duration. Out-patient treatment in an emergency room is not in itself an SAE, although the reasons for it may be.

Elective surgery, or hospital admissions and/or surgical operations planned before or during this study are not considered Aes if the illness or disease existed before the participant was enrolled in the study, provided that it did not deteriorate in an unexpected way during the study.

- Results in persistent or significant disability/incapacity.
- Is a congenital anomaly/birth defect.
- Is medically important or is a medically significant event.

Medical and scientific judgement is required to decide if prompt notification is required in situations that the investigator regards as medically important that did not strictly meet the criteria above but may have jeopardised the participant or required intervention to prevent one of the outcomes listed above, or that would suggest any significant hazard, contraindication, side effect or precaution that may be associated with the use of the IMP. Such events should also be considered as serious.

## 20.7. Recording of adverse events

For Australian sites, all events from Screening to prior to the first dose of IMP will be captured as medical history. All events occurring during and following the first administration of IMP will be reported as AEs or SAEs (if criteria met) until the completion of the End of Study Evaluation visit.

AEs that are ongoing at the End of Study Evaluation visit will be followed up until the event has resolved or stabilised. All follow-up information will be recorded in the participant's source records. All spontaneously volunteered and enquired for, as well as observed AEs, will be recorded in the participant's source records as well as the CRF.

It is preferable that AEs and SAEs be reported as diagnoses if available, rather than individual signs and symptoms. SAEs should be reported and documented in accordance with the procedures in listed below. The following data should be documented for each AE: the description of the event, start and stop dates, intensity, causality and outcome must be recorded, as well as any actions taken.

### 20.7.1. Clinical lab abnormalities and other abnormal assessments

Abnormal laboratory findings (e.g., clinical chemistry, haematology, and urinalysis) or other abnormal assessments (e.g., ECG, vital signs) per se are not reported as AEs. However, those abnormal findings that are deemed clinically significant or are associated with signs and/or symptoms must be recorded as AEs (and recorded as an SAE if they meet the criteria of being serious) as described previously. Clinically significant abnormal laboratory or other abnormal findings that are present at baseline and worsen after first dose of IMP are to be considered AEs (and SAEs if serious).

The investigator should exercise his or her medical and scientific judgment in deciding whether an abnormal laboratory finding or other abnormal assessment is clinically significant. Usually, the abnormality should be associated with a clinically evident sign or symptom, or be likely to result in an evident sign or symptom in the near term, to be considered clinically significant. A clinically significant laboratory abnormality in the absence of clinical symptoms may jeopardize the subject and may require intervention to prevent immediate consequences.

## 20.8. Reporting of serious adverse events

Any SAE must be reported by the investigator if it occurs during the clinical study or within 2 weeks of the participant having received the last dose of IMP, whether or not the SAE is considered to be related to the IMP. This shall include pregnancy in a female participant or in a female partner of a male study participant. Instances of death, congenital abnormality or an event that is of such clinical concern as to influence the overall assessment of safety, if brought to the attention of the investigator at any time after cessation of IMP administration and linked by the investigator to this study, should be reported to the sponsor.

The investigator must report an SAE on an SAE Report Form and forward the SAE Report Form, the AE form and the concomitant medication form to the sponsor or delegate **within 24 hours of becoming aware of the SAE and regardless of causality**. All pregnancies in a female participant or in a female partner of a male study participant should be reported on a Pregnancy Report Form following the same reporting process and timelines required for SAEs.

The investigator should not wait to receive additional information to document fully the event before notification of a SAE, though additional information may be requested. Where applicable, information from relevant laboratory results, hospital case records and autopsy reports should be obtained.

---

Follow-up information on SAEs must also be reported by the investigational site to the sponsor within the same time frame. If a non-serious AE becomes serious, this and other relevant follow-up information must also be provided within 24 hours of the investigator becoming aware. All SAEs will be recorded in the participant's source documents and the CRF.

It is the responsibility of the sponsor to determine whether a reported SAE fits the classification of a SUSAR (refer to Section 12.1.3). If the sponsor considers the SAE to be drug related (i.e. an adverse drug reaction), unexpected and fulfils the criteria for a Suspected Unexpected Serious Adverse Reaction (SUSAR), the sponsor has the responsibility to expedite the reporting to all concerned investigators, to the EC where required, and to the appropriate regulatory authorities within the pre-defined timelines.

The investigator must notify their EC of SAEs occurring at the site, within the time period and in accordance with requirements specified by the EC. The sponsor and/or delegate will promptly notify all relevant investigators and the regulatory authorities of findings that could adversely affect the safety of participant's, impact on the conduct of the study or alter the ethics approval/favourable opinion of the study.

## 20.9. Follow-up of adverse events and serious adverse events

All AEs and all SAEs must be followed by the investigator until resolution, or until in the opinion of the investigator, the AE has stabilised or is recognised as permanent, or until the participant is lost to follow up, whichever comes first. Follow-up investigations may be necessary according to the investigator's medical judgement.

# 21. STATISTICAL ANALYSIS

## 21.1. General considerations

An analysis of Part A will be conducted when all subjects in Part A have completed Part A.

A final analysis of Part B will be conducted when all subjects have completed Part B.

The statistical analysis principles described below will be supplemented by a comprehensive statistical analysis plan (SAP) which will be finalised before the database is locked. This will contain details of methods for handling missing data and early withdrawals. Any changes to the statistical analysis plan will be described and justified in the final report.

Descriptive statistics will be used to analyse the data in both Part A and Part B of the study. The descriptive summary for the categorical variables will include counts and percentages. The descriptive summary for the continuous variables will include number of participants (n), means, medians, standard deviations, and minimum and maximum values. Pharmacokinetic measures will be analysed as for continuous variables.

In Part A and Part B, data will be tabulated and analysed with respect to subject enrolment and disposition.

In Part A, demographic, baseline characteristics and prior medications summaries will be presented overall. Concomitant medications, PD, PK and safety measure summaries will be presented by active treatment dose, placebo and overall. Note that results for the subjects on placebo across all doses will be combined for summary purposes.

---

In Part B, demographic, baseline characteristics (including history of lumbar radicular pain) and prior medications will be presented by treatment sequence and overall. Efficacy, PD, PK, concomitant medications and safety measure summaries will be presented by treatment within each treatment period and overall.

As this is a Proof-of-Concept study, no formal statistical hypotheses are being specified although some may be investigated as part of the data presentation, in which case corresponding 95% confidence intervals will be presented for treatment differences and p-values of  $<0.05$  will be declared statistically significant. Treatment comparisons will take into account the paired nature of the treatment responses where feasible and treatment period order will be ignored in any treatment comparisons.

All data will be listed for all subjects to support each table and to present all data. All statistical analyses will be performed using SAS unless otherwise stated in the SAP.

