2.5 Changes to analyses from protocol

These changes relate to Part B of the study only.

Interim analysis:

The planned interim analysis after at least 10 subjects had completed the study was undertaken after 14 subjects completed the study. The rationale for including 14 subjects within the interim analysis was based on a number of factors, including:

- The observation that 2 of the subjects received less than the full dose (estimated to be 60-65%) due to technical issues with the infusion equipment. Both the sponsor and the PI agreed that it was wise to include at least an additional 2 subjects within the interim analysis
- At the time recruitment approached 12 completed subjects, the recruitment rate was relatively strong, which resulted in 14 subjects completing the study before the interim analysis was initiated.

The planned initial graphical outputs were produced.

No re-estimation of the sample size was undertaken. Based on: (i) the planned graphical outputs, (ii) some additional blinded post-hoc graphical presentations (not discussed in this SAP), (iii) the expectation that 17 subjects were expected to complete the study by 12 May 2023, (iv) dosing an additional 3 subjects to reach the target of 20 could take another 3-6 months, and (v) the inclusion of additional subjects would be unlikely to change any treatment signal in the data to such an extent that continuing recruitment is justified, the recommendation was made to close the study on 12 May 2023, with the last patient last visit then expected on 19 May 2023.

Final analyses:

The data presentation and analysis for the Bang Binding Index assessment has been included in this SAP as it was inadvertently missed in the previous version of the SAP.

After review of the interim analysis outputs where extensive variation in pain scores over time and an unexpected effect of being in the clinic for 24 hours possibly reducing pre-dose pain score on Day 2, particularly for pain at rest, the following decisions were made as to changes to the final analysis outputs.

- Pain at rest:
 - The mean change from baseline from 1 to 2 hours and from 4 to 6 hours are included to provide an easily interpretable summary measure of the pain response profile.
 - The area under the subject profile curve has been removed because it is less meaningful in a clinically useful interpretation of the pain response profile

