11.1.1 Biostatistical methods

Efficacy will be assessed based on the difference between treatments in the following measures:

Pain Now Scores (VAS)

“Pain now” scores, change from baseline, percentage change from baseline and summary scores (i.e. maximum change from baseline, mean change from baseline over 1 to 2 hours and mean change from baseline over 4 to 6 hours) will be listed for all study participants at each timepoint by treatment sequence.

Descriptive statistics including the number of participants, mean, standard deviation, median, minimum and maximum for the VAS “pain now” score at each timepoint along with the change from baseline and percentage change from baseline will be presented by treatment group within treatment period and overall. The mean, standard deviation, median, minimum and maximum for the change from baseline over 6 hours, the mean change from baseline over 1 to 2 hours and the mean change from baseline from 4 to 6 hours will be presented by treatment group within treatment period and overall.

Graphical presentations will include those presented for the interim analysis:

1. Individual subject VAS scores-time profiles by timepoint and by sequence (left panel LAT8881-Placebo, right panel Placebo-LAT8881)
2. Group mean VAS scores by timepoint and day, two sequences combined (one panel only)
3. Group mean VAS scores by timepoint and day in each panel, and by sequence (left panel LAT8881-Placebo, right panel Placebo-LAT8881)

Additional graphical presentations will include:

4. Individual subject change from baseline -time profiles by post-dose timepoint and by sequence (left panel LAT8881-Placebo, right panel Placebo-LAT8881)
5. Group mean change from baseline by post-dose timepoint by treatment, two sequences combined (one panel only)
6. Group mean change from baseline by post-dose timepoint and by sequence (left panel LAT8881-Placebo, right panel Placebo-LAT8881)
7. Difference between treatments in the change from baseline at each post-dose timepoint by sequence (left panel LAT8881-Placebo, right panel Placebo-LAT8881)
8. Difference between treatments in the change from baseline at each post-dose timepoint by treatment (one panel only)
9. A scatter plot for baseline scores with Placebo score on the x-axis, LAT8881 score on the y-axis, a diagonal line with slope=1 representing no difference between treatments will be overlaid on the plot, symbols and symbol colour will be used to identify treatment sequence.

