10. Maximum change from baseline will be presented using the same scatter plot format as for baseline scores
11. Mean change from baseline over 1 to 2 hours will be presented using the same scatter plot format as for baseline scores
12. Mean change from baseline over 5 to 6 hours will be presented using the same scatter plot format as for baseline scores

To estimate the difference between LAT8881 and Placebo in the change from baseline "pain now" VAS over all session time points, a generalised linear mixed effects model will be fitted. Fixed-effects will include treatment, session time point and period (i.e. Day) factors; baseline will be included as a covariate. Random effects for participants and participant by period will be included to take into account the repeated measures on each participant and the cross-over nature of the study. The covariance structure for the random effects is assumed to follow a compound symmetry structure. The estimated adjusted (least squares) mean change from baseline for each treatment at each session time, the difference between the treatments, the 95% confidence interval for the difference and the p value for the difference will be presented. A p value of <0.05 will be declared statistically significant. The model assumes no carry-over treatment effect and assumes that any period (i.e Day) effect will affect subjects in both treatment sequences in a similar manner.

The same model will be fitted to the change from baseline "pain on leg raise" VAS scores. As reflected in the scientific literature and regulatory authority guidelines, what constitutes a minimally significant change in baseline pain score can vary from subject-to-subject, whether the pain is acute or chronic, and on the mechanism of the pain. For the purposes of this study, the sponsor considers a 0.9 cm reduction to represent a minimally clinically significant change in pain as reported on the VAS, with the desired target reduction from baseline in the range of 0.9 to 3 cm.

Provocation Assessment with VAS

The pain on leg raise VAS score, change from baseline, percentage change from baseline, maximum change from baseline, mean change from baseline from 1 to 2 hours and mean change from baseline from 4 to 6 hours will be listed for all study participants at each timepoint by treatment sequence as for the "pain now" endpoints. Descriptive summary tables and analyses will be as per the "pain now" endpoints.

Patients general impression of change

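### Protocol 21.1 tells the analyst to ignore period; the SAP model fits it without declaring the change, and the pooled descriptive treatment differences remain unadjusted for Day

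*Protocol*

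**What the plan says.** Protocol 21.1 gives two rules for treatment comparisons. The first concerns pairing: "Treatment comparisons will take into account the paired nature of the treatment responses where feasible". The second follows in the same sentence: "treatment period order will be ignored in any treatment comparisons". Protocol 21.5 then plans, at each timepoint, the difference between treatments and the difference in change from baseline, with mean and SD, both overall and within period.

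SAP 11.1.1 takes a different line for its model of pain now, repeated for pain on leg raise: "Fixed-effects will include treatment, session time point and period (i.e. Day) factors; baseline will be included as a covariate". SAP 2.5, the section that records departures from the protocol for Part B, does not mention the period term.

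Outside the model, SAP 11.1.1 tabulates scores, changes, peak change and the window means by treatment, within period and overall. Two figures pool the sequences. Figure 5 is "Group mean change from baseline by post-dose timepoint by treatment, two sequences combined (one panel only", and figure 8 is "Difference between treatments in the change from baseline at each post-dose timepoint by treatment (one panel only". Figures 6 and 7 repeat them by sequence.

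SAP 2.5 also reports, from the interim outputs, "an unexpected effect of being in the clinic for 24 hours possibly reducing pre-dose pain score on Day 2", and that "17 subjects were expected to complete the study by 12 May 2023".

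**The concern.** Two documents that should agree give opposite instructions on a basic feature of a crossover analysis, and the section meant to reconcile them is silent. A reader cannot tell which rule governs.

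This matters in practice because the pooled outputs still behave as the protocol sentence directs. In a two-period crossover, a Day effect pushes the paired differences in opposite directions in the two sequences. When the sequences are simply pooled, that push appears partly as a shift in the mean difference, if the sequences are unequal in size, and partly as extra spread, whether or not they are equal. The sponsor itself suspects a Day effect. Peak change and the 1–2 hour and late-window means receive only descriptive summaries, so for them no period-adjusted result is planned anywhere.

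**Working it through.** The documents give no SD, no Day-effect size and no derivation of the sample size, so there is no planned figure to reproduce. What follows is standard 2×2 crossover algebra with stated assumptions.

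**Inputs from the documents.** Planned allocation 10 + 10 (SAP 2.2). Expected completers 17, with no sequence split given (SAP 2.5). Two participants under-dosed, so a per-protocol set of 15 is possible (SAP 2.5). Smallest change the sponsor regards as clinically significant, 0.9 cm (SAP 11.1.1). A separate baseline for each period in Part B (SAP 3.2.1 and 3.2.2).

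**Assumed.** D (Day 2 minus Day 1, on the scale analysed) = 0.5 or 1 cm, with 0.9 and 2 cm used in places below. SD of the within-participant treatment difference = 1.0, 1.5 or 2.0 cm. Sequence splits as shown.

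**Where D can enter.** Change from baseline uses each period's own baseline, so a constant Day shift in pain level cancels from change scores. D is therefore either a Day effect on raw VAS scores or a Day effect on the post-dose change. The second could arise if a lower Day 2 baseline leaves less room to fall.

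**Mean.** With T the true LAT8881 minus placebo difference, the paired difference averages T − D when LAT8881 comes first (LP) and T + D when placebo comes first (PL). The pooled mean is T + D(nPL − nLP)/N.

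- 10/10: no shift.
- 9/8: D/17 = 0.059 D, which is 0.06 cm at D = 1 and 0.12 cm at D = 2.
- 10/7: 3/17 = 0.176 D.
- Per-protocol set of 15, split 9/6: 3/15 = 0.20 D.

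The equal-weight average of the two sequence means is [(T − D) + (T + D)]/2 = T for any split.

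**Spread.** The expected variance of the pooled paired differences is SD² + D² × 4·nPL·nLP/[N(N − 1)]. The multiplier of D² is 288/272 = 1.059 at 9/8 and 400/380 = 1.053 at 10/10. Balance therefore does not remove the inflation. For example, SD 2 with D = 0.9 becomes 2.20 in both cases.

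**Standard error at 9/8.** Adjusted: (SD/2)·√(1/9 + 1/8) = 0.243 SD. Ignoring period: √(SD² + 1.059 D²)/√17.

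| SD (cm) | Adjusted SE | Ignoring period, D = 0.5 | Ignoring period, D = 1 |
|---|---|---|---|
| 1.0 | 0.243 | 0.273 (+12%) | 0.348 (+43%) |
| 1.5 | 0.364 | 0.385 (+6%) | 0.441 (+21%) |
| 2.0 | 0.486 | 0.501 (+3%) | 0.546 (+12%) |

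**Direction of the error.** A paired test that ignores period is conservative. At SD 2 and 9/8, the simulated type I error (200,000 runs) was 0.033 at D = 0.9 cm, against a nominal 0.05.

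**The case against.** The strongest reply is that the SAP's only planned inference already does the right thing. The model includes Day, has participant and participant-by-period random effects, and states its assumption that Day acts alike in both sequences. The pooled tables and figures have within-period or by-sequence counterparts, and the scatter plots mark sequence precisely because a Day effect is suspected. Unadjusted descriptive summaries beside an adjusted model are ordinary practice. All of this stands, and it confines the point to the contradiction and the pooled descriptive differences.

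Four stronger readings are tempting, and the documents do not support them.

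- *That the trial's main treatment estimate is biased by Day.* It is not, for an additive Day effect, because the model adjusts for it.
- *That the odd number of completers is the root of the problem.* Seventeen is an expected count and the split is not stated. At 9/8 the shift is only D/17, and the spread inflation is almost the same at 10/10.
- *That power drops sharply.* At SD 1.5 and D = 1 cm, a noncentral-t approximation gives 64% adjusted and 48% unadjusted for 0.9 cm. The SAP plans no unadjusted paired test, however, and the approximation treats D as random noise. Direct simulation gives 54% or 42%, depending on the sign of D.
- *That a Day effect on the analysed change scores has been established.* SAP 2.5 says only that one was possible, on pre-dose pain, and gives no size.

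A reader might also infer that the period term was added because of the interim outputs. The documents do not say when or why it was added.

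**Conclusion.** The point holds in a limited form. The protocol and SAP contradict each other on period, and SAP 2.5 does not declare the change. The model results need no correction for this. The pooled treatment differences outside the model carry any Day effect on their own scale. For peak change and the window means, no adjusted alternative is planned.

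The effect on the mean is small for a near-even split, and reaches 18–20% of D only under the hypothetical 10/7 or 9/6 splits. The effect on spread is the larger one: 3–12% on the standard error at D = 0.5 cm and 12–43% at D = 1 cm, over SDs of 2.0 to 1.0 cm at 9/8. These percentages illustrate what the protocol's rule would produce. They rest on assumed values of D, SD and split. For change scores they also require that Day alters the post-dose change and not merely the level of pain.

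**What to change.** 1. Delete the period clause from Protocol 21.1, or state in SAP 2.5 that it is replaced by the period-adjusted model, with the reason.
2. For figure 8 and the overall treatment differences, including peak change and the window means, report the equal-weight mean of the two sequence-specific mean differences, with the SD pooled within sequence.
3. Keep figure 5 and the raw overall means by treatment, labelled as unadjusted for period. Figure 5 shows treatment means, so a difference cannot stand in for it.
4. Keep all by-sequence and by-period outputs.

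The cost is SAP wording and a change in how a few pooled differences are computed, with no new data. If there is no Day effect, the adjustment costs almost nothing: at 9/8 the standard error is 0.2430 SD instead of SD/√17 = 0.2425 SD, with one fewer degree of freedom (15 instead of 16).
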